 feasible, preferably within 7 calendar days of the DSMB meeting, the Summary
 Report as outlined above, outlining the concerns and the basis for any
 recommendations that the DSMB has made in response to the concerns.
 Adverse event reporting will be consistent with NHLBI policy.

Reports to the DSMB

For each meeting, unblinded analyses and reports will be prepared by the DSMB statistician as this is a double blinded study and the PI and study staff will not have access to the data required to prepare these reports. Reports will be prepared according to the DSMB's **recommendations** regarding which data should be presented and the format of the data presentation.

Statistical Monitoring Guidelines

The DSMB will review the adequacy of the statistical monitoring plan. The final plan, whether part of a research protocol or separate document, will be maintained as an appendix to this Charter. The DSMB should discuss the statistical monitoring procedures that will be followed to guide recommendations about termination or continuation of the trial. These procedures could include guidelines for termination due to safety reasons.

ADVERSE EVENTS AND REPORTING

This section defines the types of safety data that will be collected under this protocol and outlines the procedures for appropriately collecting, recording and reporting those data.

Definitions

Adverse Event

For the purposes of this protocol, an adverse event will be defined as any adverse medical change (i.e., de novo or increased severity in a preexisting condition) from the subject's baseline condition, that occurs during the course of the clinical study, after receiving Regadenoson infusion through Day 30, whether considered device related or not and meeting the protocol requirements.

Anticipated symptoms caused by the COVID-19 infection and standard care are expected to occur between time of Regadenoson infusion and Day 30. The following are examples of anticipated events caused by the COVID-19 infection and standard care are medications not considered AE's:

- Fever
- Incubation related inflammation, sour throat
- Shortness of breath
- Pneumonia
- Renal insufficiencies secondary to medications
- Sleep issues (insomnia)
- Gastrointestinal discomfort (i.e. constipation, decreased appetite, diarrhea)
- Pulmonary observations (i.e. wheezing, cough)
- Neurological observations (i.e. hallucinations, confusion)
- Renal observations (i.e. urinary tract infections, urinary retention)

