 There may be additional expected events not listed which may be documented in the patient's medical record by the investigator.

The events above are not considered adverse events for this study and will not be recorded.

Serious Adverse Event

- A Serious Adverse Event (SAE) is one that:
- Leads to death;
- Leads to serious deterioration in the health of the study patient that:
 - Results in life-threatening illness or injury;
 - Results in a permanent impairment of a body structure or a body function;
 - Requires in patient hospitalization or prolongation of existing hospitalization;
 - Results in medical or surgical intervention to prevent permanent impairment to body structure or a body function;
- Results in congenital anomaly/birth defect
- Significant medical event.

NOTE: A planned hospitalization for a pre-existing condition, or anticipated procedures such as routine transplant related biopsy or elective surgery will not be considered serious adverse events.

Note that seriousness and severity are separate concepts. The term "severe" refers to the intensity of a specific event; a severe event may be of minor medical significance (e.g., a severe leg cramp). The term "serious" is based on an outcome or action criteria that are usually associated with events that pose a threat to the patient's life or functioning. An event that is mild in severity is serious if it leads to one of the outcomes defined above.

Unanticipated problem involving risks to subjects or others (UP) - Any incident, experience or outcome that meets all the following criteria:

- Unexpected (in terms of nature, severity, or frequency) given:
- The research procedures that are described in the protocol related-documents, such the IRB-approved research protocol and the informed consent form document and.
- The characteristics of the subject population being studied;
- Related or possibly related to the subject participation in research; and

 Suggests that the research places subjects or others at a greater risk of harm (including physical, psychological, economic, or social harm) related to the research than was previously known or recognized.

Grading of Adverse Events – Events will be graded by using the Common Terminology Criteria for Adverse Events (CTCAE) Criteria version 4.03.

Attribution Assessment

Attribution – the determination and documentation of whether an adverse event is related to Regadenoson infusion.

Attribution Categories:

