- 1. Not Related Event clearly related to other factors (e.g., clinical state, other therapies; concomitant drugs)
- 2. Possibly Related Sequence of event is compatible with device, or procedure, but could have been produced by other factors
- Probably Related Sequence of event is compatible with device, or procedure and cannot be explained by other factors without much doubt
- 4. Definitely Related Sequence of event is compatible with device or procedure and beyond doubt cannot be explained by other factors

Severity

The degree of severity of the AE to the subject's health will be documented on the AE CRF.

Grade 1 Mild; asymptomatic or mild symptoms; clinical or diagnostic observations only; intervention not indicated.

Grade 2 Moderate; minimal, local or noninvasive intervention indicated; limiting age-appropriate instrumental ADL.

Grade 3 Severe or medically significant but not immediately life-threatening; hospitalization or prolongation of hospitalization indicated; disabling; limiting self-care ADL.

Grade 4 Life-threatening consequences; urgent intervention indicated.

Grade 5 Death related to AE.

Unanticipated Adverse Device Effect (UADE)

A UADE is any serious adverse effect on health or safety, any life-threatening problem or death caused by, or associated with a device, if that effect, problem, or death was not previously identified in nature, severity, or degree of incidence in the investigational plan (e.g., ICF, Study Protocol, Instructions for Use (IFU), publications, etc.) or any other

unanticipated serious problem associated with a device that relates to the rights, safety, or welfare of subjects.

Adverse Event Recording

All adverse events will be collected starting at time of infusion through POD 30. Events that meet the definition of "anticipated" (see section 8.1.1) will not be recorded as adverse events unless the event meets the criteria of a Serious Adverse Event. Adverse events should be recorded on a case report form and will be assessed for seriousness, severity, attribution and expectedness by the site Principal Investigator.

Reporting Requirements

Expedited Reporting

The following events require **expedited reporting**, i.e., notification to the study monitoring team within 24 hours and DSMB and NHLBI within at least 7 calendar days of learning of the event's occurrence:

- All Serious Adverse Events that are at least possibly related/associated with the study device.

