- All unanticipated problems and unanticipated adverse device effects that occur within 30 days of Regadenoson infusion.
- All (fatal) events within 30 days of Regadenoson infusion.

Efforts should be made to report expedited events to the DSMB and NHLBI as soon as possible but within at least 7 days. All other events will be recorded in the electronic data capture system.

Events that require expedited reporting must be reported by email or telephone within 24 hours to:

Office of Accountability and Compliance

University of Maryland, Baltimore

[contact]

[contact]

Expedited reports will also be submitted to the DSMB and NHLBI (see Table 4) within 7 calendar days of learning of the event's occurrence.

Reporting to the UMB HSR-IRB and DSMB

The Principal Investigator or designee is responsible for reporting SAEs and unanticipated problems to the site IRB according to the participating site institutional guidelines.

Table 4. DSMB and NHLBI Reporting Requirements

DSMB and NHLBI							
Type of Event	To whom will it be reported:	Time Frame for Reporting	How reported?				
All Adverse Events	DSMB and NHLBI	30 calendar days prior to scheduled DSMB meetings	DSMB report will include listing of all Adverse Events				
Reportable SAE's and Unanticipated Problems	DSMB and NHLBI	7 calendar days of knowledge of the event	Report to Designated DSMB member and NHLBI				
DSMB Reports	IRB	15 calendar days of the study team receiving the report	Copy of DSMB report				

Reporting to the FDA

The Sponsor for the study is responsible for providing safety updates to the FDA per the following guidelines (Table 5). The reporting times refer to the time the study team received knowledge of the AE.

Table 5. FDA Reporting Requirements

UMB PI HELD IDE						
Type of Event	To whom will it be reported:	Time Frame for Reporting	How reported?			
Life-threatening and/or fatal unexpected events related or possibly related to the use of the investigational agent.	FDA	Within 7 calendar days of the study team learning of the event	Form FDA 3500A (MedWatch) or narrative			
Serious, unexpected and related or possibly related adverse events	FDA	Within 15 calendar days after the study team receives knowledge of the event	Form FDA 3500A (MedWatch) or narrative			

Unanticipated Adverse Device Effects	FDA	Within 10 working days of the study team learning of the event	Form FDA 3500A (MedWatch) or narrative
All adverse events	FDA	Annually	IDE annual report

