APPENDIX A: NIAID 8-Point Ordinal Scale for COVID-19

The ordinal scale is an assessment of the clinical status at the first assessment of a given study day. The scale is as follows:

- 1. Death;
- 2. Hospitalized, on invasive mechanical ventilation or extracorporeal membrane oxygenation (ECMO);
- 3. Hospitalized, on non-invasive ventilation or high flow oxygen devices;
- 4. Hospitalized, requiring supplemental oxygen;
- 5. Hospitalized, not requiring supplemental oxygen, requiring ongoing medical care (COVID-19 or otherwise);
- 6. Hospitalized, not requiring supplemental oxygen, and no longer requires ongoing medical care (e.g., patient still admitted for isolation purposes only).
- 7. Not hospitalized, limitation on activities;
- 8. Not hospitalized, no limitations on activities.

Table 1, Detailed Grading Scales of Toxicity of Regadenoson

	CTCAE v4.0	Grade 1	Grade 2	Grade 3	Grade 4	Grade
1	Acute coronary syndrome	-	Symptomatic, progressive angina; cardiac enzymes normal; hemodynamicall y stable	Symptomatic, unstable angina and/or acute myocardial infarction, cardiac enzymes abnormal, hemodynamically stable	Symptomatic, unstable angina and/or acute myocardial infarction, cardiac enzymes abnormal, hemodynamically unstable	5 Death
2	Atrial fibrillation	Asymptom atic, interventio n not indicated	Non-urgent medical intervention indicated	Symptomatic and incompletely controlled medically, or controlled with device (e.g., pacemaker), or ablation	Life-threatening consequences; urgent intervention indicated	Death
3	Atrial flutter	Asymptom atic, interventio n not indicated	Non-urgent medical intervention indicated	Symptomatic and incompletely controlled medically, or controlled with device (e.g., pacemaker), or ablation	Life-threatening consequences; urgent intervention indicated	Death
4	Atrioventric ular block complete	-	Non-urgent intervention indicated	Symptomatic and incompletely controlled medically, or controlled with device (e.g., pacemaker)	Life-threatening consequences; urgent intervention indicated	Death
5	Atrioventric ular block first degree	Asymptom atic, interventio n not indicated	Non-urgent intervention indicated		-	-
6	Cardiac arrest	-	-	-	Life-threatening consequences; urgent intervention indicated	Death
7	Heart failure	Asymptom atic with	Symptoms with mild to	Severe with symptoms at rest	Life-threatening consequences;	Death

		laboratami	madarata	or with minimal	urgont	
		laboratory	moderate	or with minimal	urgent	

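### Non-serious kidney impairment and wheezing leave the adverse-event record when blinded staff attribute them to COVID-19 or standard care, although Table 1 grades both as Regadenoson toxicity

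*Combined protocol and SAP*

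**What the plan says.** All of this is in the combined protocol and SAP.

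- **Definition.** Volume 3, Adverse Events and Reporting, Definitions, counts any adverse medical change from baseline after the infusion through Day 30, "whether considered device related or not".
- **Exception.** The same section then gives examples of anticipated events caused by COVID-19 and standard care that do not count. Among them are "Renal insufficiencies secondary to medications" and pulmonary observations, with wheezing and cough as the examples. It closes: "The events above are not considered adverse events for this study and will not be recorded".
- **Override for serious events.** Adverse Event Recording softens this: anticipated events "will not be recorded as adverse events unless the event meets the criteria of a Serious Adverse Event".
- **Attribution.** Attribution Assessment has four categories. Not Related covers events explained by clinical state, other therapies or concomitant drugs. Possibly Related covers events compatible with the intervention that might also have another cause.
- **Toxicity table.** Table 1 is titled "Detailed Grading Scales of Toxicity of Regadenoson". Row 17 grades acute kidney injury, starting at a creatinine rise above 0.3 mg/dL. Row 18, bronchial obstruction, gives mild wheezing as a Grade 2 example. Row 19 is bronchospasm.
- **What the board receives.** Table 4 says that the "DSMB report will include listing of all Adverse Events".

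**The concern.** Two event types that the protocol grades as toxicity of the study drug also stand on a list of events that need not be written down. Whether they are written down depends on a judgement of cause, made in a double-blind trial by staff who do not know the treatment. The protocol itself says that the kidney judgement is difficult: the pharmacokinetic summary in Volume 2 notes that both COVID-19 and standard-of-care treatment may affect renal function. For the airways, the dose justification names bronchoconstriction as a rare Regadenoson side effect and keeps aminophylline at hand for it.

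The usual order is to record first and attribute afterwards. The list reverses that order for these events. An error of attribution then leaves no line for the unblinded DSMB statistician to compare by arm. Safety is part of the primary objective, and Sample Size and Statistical Analysis gives the safety analysis priority so that the trial can expand to several sites.

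**Working it through.** The plan gives no figure on this point, so the check is mainly a comparison of texts.

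**1. Path of one event.** Take a patient on Regadenoson whose creatinine rises by 0.4 mg/dL, without meeting any criterion for a serious event.
- By Table 1, row 17, this is at least Grade 1 kidney injury.
- If staff think that the infusion may have contributed, it can be recorded as Possibly Related.
- If they put it down to another medicine, it falls under the renal item on the anticipated list. It is not an adverse event and is not recorded.
- In the second case it never reaches the Not Related category, which exists for exactly that opinion, and it cannot appear in the Table 4 listing.

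Mild wheezing follows the same path if noted as an observation. If coded as bronchospasm (row 19), it is not on the list and stays.

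**2. What else could show the event.** Table 2 schedules laboratory tests and physical examination at screening and D1. From D3 on, both carry an asterisk: not required, recorded if available. Footnote 4 puts creatinine in a panel that carries the words when available. The items required at every visit from D1 to D30 are AE assessment and vital/respiratory status. So there is back-up around the infusion and D1, and less afterwards.

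**3. Effect on the recorded difference.** Let b be the proportion with a background event, e the extra proportion with a drug-caused event (assumed to fall in other patients), fb the share of background events filtered out (assumed equal in both arms), and fd the share of drug-caused events filtered out by misattribution.
- Recorded, control: b(1 − fb)
- Recorded, Regadenoson: b(1 − fb) + e(1 − fd)
- Difference: e(1 − fd)

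The background filter cancels. Only misattributed drug-caused events shrink the difference. With 40 patients randomized equally there are 40/2 = 20 per arm, so one such patient is 1/20 = 5 percentage points.

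**4. Illustration, all inputs assumed.** The documents give none of b, e, fb or fd. Take b = 0.40 and e = 0.20. Without filtering, 0.40 against 0.60 gives SE = √(0.24/20 + 0.24/20) = 0.155 and z = 0.20/0.155 = 1.29. With fb = 0.75:

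| fd | control | Regadenoson | difference | SE | z |
|---|---|---|---|---|---|
| 0.10 | 0.10 | 0.28 | 0.18 | 0.121 | 1.49 |
| 0.25 | 0.10 | 0.25 | 0.15 | 0.118 | 1.27 |
| 0.50 | 0.10 | 0.20 | 0.10 | 0.112 | 0.89 |

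The difference always shrinks when fd > 0. The contrast can sharpen, because removing background events removes noise, or weaken. Here z falls below 1.29 once fd exceeds about 0.24; the break-even is about 0.09 for fb = 0.50 and 0.02 for fb = 0.25. The table shows direction only and does not estimate what would happen in this trial.

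**The case against.** The strongest reply is that the exclusion is conditional. It removes only events caused by COVID-19 or standard care, and an event of uncertain cause can be read as Possibly Related and recorded. That stands, and it narrows the point to events that staff attribute firmly, and wrongly, to something other than the drug.

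The wheezing conflict is also thinner than the renal one. Row 18 mostly describes mechanical obstruction, and the known drug effect, bronchoconstriction, fits row 19 better. Asthma, COPD and emphysema are excluded. This stands too; what remains is wheeze noted as a bare observation.

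On the kidney, the protocol reports no renal toxicity in the lung-transplant trial, and no serious adverse events through 24 hours in a 504-patient placebo-controlled trial in renal impairment. Patients with GFR below 60 are excluded, and treatment lasts under 7 hours. This lowers the likely number of events. The 504-patient result, however, concerns serious events, which the list does not filter.

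The DSMB also reviews other safety data, may request any relevant data and decides the content of its reports, so it could ask for creatinine by arm without an amendment. That is a real route for laboratory values, but no comparable route is described for wheezing, and it does not restore an adverse-event line. The rule that stops the infusion for renal impairment protects only during the infusion.

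Lastly, leaving out non-serious events expected from the disease is a deliberate choice with an override for serious events. As a general policy that is defensible. It fits poorly for items that the same document grades as toxicity of the study drug.

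**Conclusion.** The inconsistency is real and modest. Non-serious renal insufficiency attributed to medication, and wheezing attributed to COVID-19 or standard care, are kept out of the adverse-event record, while Table 1 grades kidney injury and mild wheezing as Regadenoson toxicity. A drug-caused event misattributed this way would be absent from the DSMB's listing. The likely effect is limited to mainly Grade 1 and 2 events. Its size cannot be derived from the documents; the firm results are the factor (1 − fd) on the drug-caused excess, given the assumptions stated with it, and the step of 5 points per patient.

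A reader might infer more, and the documents do not support it:
- *That all such events vanish.* Serious events, events coded as bronchospasm and events judged possibly related are kept.
- *That filtering as such biases the comparison.* Filtering true background events equally in both arms leaves the difference unchanged.
- *That the board could not see renal toxicity.* Creatinine around the infusion and at D1, and the board's right to other data, give partial cover.
- *That the safety pausing or stopping rules are undermined.* They count serious cardiovascular and persistent intolerable side effects; kidney injury and wheezing are not named among these, and nothing is claimed here about those rules.

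**What to change.** Delete the renal item and wheezing from the anticipated-event list. Record both in both arms whatever the presumed cause, grade them by Table 1, and assign cause afterwards with the existing categories, Not Related or Possibly Related.

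Optionally, tabulate kidney-injury grade by arm for the DSMB from the creatinine values that exist, against baseline. Baseline and D1 are scheduled and later values are recorded only if available, so this table would be incomplete after D1. It supplements the change to the list and does not replace it. No new mandatory testing is proposed.

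The cost is two deletions and, if wanted, one derived table. The downside is a few more background adverse-event lines in 40 patients.

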In cohort 1, we will enroll patients to test the safety, tolerability and toxicity in moderate to severe COVID-19 patients. Initial subjects in cohort 1 will receive a loading dose of 5.0 μ g/kg (not to exceed 400 μ g) over 30 minutes followed by a low dose infusion of 1.44 μ g/kg/hr. Toxicity of Regadenoson treatment will be graded by using the Common Terminology Criteria for Adverse Events (CTCAE) Criteria version 4.03 in this trial. If two dose limiting toxicities occur at a loading dose of 5.0 μ g/kg then the loading dose will be halved to 2.5 μ g/kg and enrollment will continue. If two dose limiting toxicities occur at a loading dose of 2.5 μ g/kg then the Data and Safety Monitoring Board (DSMB) will convene to determine if the study should continue and omitting the loading dose may be considered. Alternatively, the DSMB will convene after 5 out of 5 patients or 5 out of 6 patients tolerate a given loading dose to make a determination on moving forward to cohort 2. Otherwise, the trial will be terminated. (please see the details in the Detailed DSMB Plan section)

The sickle cell trial and our phase 1 trial in lung transplant patients did not show any renal/hepatic toxicity. Because COVID-19 itself may cause renal injury, we will closely monitor the renal and hepatic function of these patients per their standard of care. To assess safety of each subject, we will tabulate sequentially the number of participants

who unexpectedly experience serious cardiovascular side effects or persistent (> 30 min) intolerable side effects. If at any point in the accrual, the posterior probability exceeds 90% that the risk of at least one serious side effect for participants in the Regadenoson arm is more than 10 percentage points greater than in the standard care arm, we will stop the trial.

Adverse Event (AE) Recording and Reporting:

All adverse events will be collected starting at time of consent through POD 30. Adverse events will be recorded on a case report form and will be assessed for seriousness, severity, attribution and expectedness by the site Principal Investigator. A serious cardiovascular side effect is defined as a sustained change (> 5 minutes) in systolic blood pressure >30 mm Hg or systolic blood pressure <75 mm Hg, tachycardia >130 bpm, or bradycardia <40 bpm.

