The primary outcome is the proportion of patients alive and free of respiratory failure through the 30-day trial. The total sample size of 40 participants will be randomized equally between the usual care and Regadenoson groups, using a randomly permuted block design, with random block sizes of 2 and 4. This plan will be generated by the study statistician. Within each group, the primary outcome proportion can be estimated with a standard error of no more than 11 percentage points; the difference between the groups can be estimated with a standard error that is no more than 16 percentage points. These calculations are based on the most conservative estimate in terms of standard error, using a proportion of 50% in each group. If, as expected, the proportions in each group are greater, such as 80% in usual care and 90% in the Regadenoson group, the difference can be estimated with a standard error of 11 percentage points. While these are relatively large standard errors, they are adequate to meet the objective suggested by the IND review, providing estimates of outcome proportions to be used in a larger trial.

To assess safety, the DSMB statistician will tabulate sequentially the proportion of participants in each group who unexpectedly experience serious cardiovascular side effects or persistent (> 30 min) intolerable side effects, based on clinical experience with Regadenoson. Intolerable side effects include headache or dyspnea. If the lower bound of a one-sided 80% confidence interval for the difference in proportions exceeds 10%, we will pause the trial, examine the adverse event profiles, and consider modifying dosing. With this rule, if the true proportion of patients who experience serious side effects is 20% in each group, there is a 16.5% chance that the trial will be paused; if the

true proportion with Regadenoson is 40%, there is a 58% chance the study will be paused.

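### The pause boundary counts persistent dyspnea, but the adverse event section says not to record non-serious shortness of breath attributed to COVID-19 or standard care, so possibly drug-related dyspnea can be screened out before attribution is documented

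*Combined protocol and SAP*

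**What the plan says.** The pause rule is in Sample Size and Statistical Analysis. The DSMB statistician tabulates, by group, the participants "who unexpectedly experience serious cardiovascular side effects or persistent (> 30 min) intolerable side effects", a class that the text ties to prior clinical experience with the drug. It adds: "Intolerable side effects include headache or dyspnea". The trial pauses if the lower limit of a one-sided 80% confidence interval for the difference exceeds 10%. The stated pause chance is 16.5% if the true rate is 20% in both groups and 58% if it is 40% on Regadenoson. Safety Assessments has the same event class in view ("we will tabulate sequentially the number of participants"), although its stopping sentence speaks of a serious side effect.

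Volume 3, Adverse Events and Reporting, defines an adverse event to include a change that is "de novo or increased severity in a preexisting condition". It then carves out a list, introduced by "The following are examples of anticipated events caused by the COVID-19 infection and standard care", which contains "Shortness of breath". The list closes with "The events above are not considered adverse events for this study and will not be recorded". Adverse Event Recording repeats the exclusion and excepts only events that meet the serious criteria. Table 4 gives the DSMB a listing of all adverse events.

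**The concern.** One of the two symptoms named for the boundary also stands on the do-not-record list. Which text applies depends on cause: the boundary concerns side effects, and the carve-out concerns effects of the disease or of standard care. In this trial that split is hard to make. Treatment is double-blind, and every patient has COVID-19 of moderate or severe grade.

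The order of steps is the weak point. Attribution is defined as a determination made on an adverse event. Someone must therefore decide that an episode of dyspnea is not due to COVID-19 before it becomes an adverse event whose cause can be documented. The Possibly Related category is meant for events that fit the intervention but might have another explanation. Dyspnea in these patients fits that description, yet it can be removed before the category is ever used, and no trace of the decision is required.

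Safety stands first in the primary objective, and the stated pause chances presuppose that boundary events are captured.

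**Working it through.** **Step 1: follow one episode through the text.** Take non-serious dyspnea lasting over 30 minutes, cause uncertain.

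- Sample Size and Statistical Analysis: it counts if it is a side effect.
- Adverse Event definition: it is not recorded if it is taken to be due to COVID-19 or standard care.
- Adverse Event Recording: the serious-event exception does not apply.
- Attribution Assessment: it is reached only if the episode was first called an adverse event.
- Table 4: the DSMB listing holds adverse events only.
- Table 2, note 3: vital signs such as respiratory rate and oxygen saturation are recorded. The symptom and its duration are not mentioned, and the 30-minute criterion needs the duration.

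**Step 2: reproduce the stated pause chances.** Inputs from the plan: 20 per arm, permuted blocks of 2 and 4, one-sided 80% (z = 0.8416), margin 10 points, DSMB meetings at 15, 25 and 40 enrolled. The interval method and the looks behind the stated figures are not given. I assume an unpooled Wald bound at those three meetings:

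L = pR − pU − 0.8416 × √[pR(1 − pR)/nR + pU(1 − pU)/nU]; pause if L > 0.10.

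Over 60,000 simulated trials (Monte Carlo error about 0.2 points) this gives about 16.7% at 20% v 20% and 60% at 20% v 40%. Fixed splits of 8/7, 13/12 and 20/20 give 16.1% and 58.4%. The stated 16.5% and 58% are reproduced closely enough.

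**Step 3: how few events matter.** At 20 per arm with 4 usual-care patients counted:

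- 8 on Regadenoson: L = 0.20 − 0.8416 × √(0.24/20 + 0.16/20) = 0.20 − 0.119 = 0.081, no pause.
- 9 on Regadenoson: L = 0.25 − 0.8416 × √(0.2475/20 + 0.16/20) = 0.25 − 0.120 = 0.130, pause.

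One uncounted patient can change the result.

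**Step 4: size of the loss, with assumed shares.** Serious cardiovascular effects and headache are not on the list. Only patients whose sole boundary event is non-serious dyspnea, and whose cause is misjudged, can be lost. Let d be the dyspnea-only share of boundary events and m the share of these misjudged, equal in both arms. Recorded rate = true rate × (1 − d × m). True rates are 20% v 40%.

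| d | m | Recorded rates | Pause chance |
|---|---|---|---|
| 0 | 0 | 20% v 40% | 60% |
| 10% | 25% | 19.5% v 39% | 59% |
| 25% | 50% | 17.5% v 35% | 54% |
| 50% | 50% | 15% v 30% | 49% |

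Other look schedules shift the level but not the pattern. For the four rows in order, a final look only gives about 44, 43, 37 and 31%; a look after every patient from the 8th gives about 72, 72, 67 and 61%. Neither schedule matches the stated 58%.

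**Step 5: the opposite case.** Suppose only background dyspnea is dropped, so that 25%, 50% or 100% of background events vanish and drug-caused events stay. With a fixed 20-point drug excess the pause chance is about 61, 64 and 68%. If the drug acts independently on 25% of patients (assumed; 1 − 0.80 × 0.75 = 0.40), it is about 64, 69 and 83%. It does not fall.

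**The case against.** The strongest reply is that the two texts do not collide. The boundary counts side effects in the light of experience with the drug, the carve-out removes effects of disease and usual care, and the word unexpectedly fits the same split. That stands as far as it goes: dyspnea already judged drug-related is not excluded. It does not say how the judgement is made or documented, and the text gives no rule for making it, such as a time window around the infusion.

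Other text softens the conflict:

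- The general definition covers new or worsened conditions, but the carve-out follows directly after it.
- The serious criteria end with an open category for significant medical events.
- Expedited Reporting says that all other events go into the data capture system, without saying whether the anticipated list is included.
- The board's recommendations govern the reports "regarding which data should be presented and the format of the data presentation", but a board cannot be shown what was not recorded.
- Table 1 grades bronchospasm and bronchial obstruction, so some respiratory drug effects have a category. Plain dyspnea has no row.
- The DSMB may pause or halt at any time, so the boundary is not the only safeguard.

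The case report form and the charter appendix with the monitoring plan are not in the file and may say more.

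A reader might infer that the boundary is blind to dyspnea, or that the pause chance collapses. Neither is supported. The exclusion is by cause, serious events are kept, the tabulation's data source is not stated, and losing a quarter or half of all boundary events would need far more than dyspnea alone to be affected or very frequent misjudgement.

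**Conclusion.** The passages need reconciling. As written, a blind and undocumented judgement of cause decides whether non-serious dyspnea reaches the adverse event listing sent to the DSMB. Loss from that listing is a direct consequence whenever possibly drug-related dyspnea is put down to COVID-19. Loss from the boundary count is a risk only, because the plan does not name the source of that count.

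The documents do not fix the size or even the direction of the effect. Under the assumed shares of 10% to 25% dyspnea-only events with 25% to 50% misjudged, detection at 20% v 40% falls from about 60% to between 54% and 59%. About 49% needs a 50% share with half misjudged. If only background events are dropped, detection does not fall. These figures also rest on the assumed Wald bound, the three looks, and equal misjudgement in both arms. This should be fixed because it bears on the trial's main numerical safety rule and is cheap to repair. My confidence is medium.

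**What to change.** Reconcile Safety Assessments, Sample Size and Statistical Analysis, and Adverse Events and Reporting:

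1. Exempt new or worsened dyspnea lasting over 30 minutes from the do-not-record rule. Record it in both arms with onset, duration and grade, and document attribution afterwards.
2. Name this record as the data source for the boundary.
3. State in advance, identically for both arms, which recorded dyspnea counts: the time period, the attribution categories, and whether unexpectedly excludes anticipated dyspnea.
4. Say whether the other events that go into the data capture system include the anticipated list.

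The cost is protocol wording and more event entry. Item 3 involves a real trade-off. If all-cause dyspnea is counted and the background rate rises to 30% or 40%, the false-pause chance goes from about 17% to about 19% or 20.5%. Detection may also fall, because a patient already counted for background dyspnea cannot be counted again. With independent drug action on 25% of patients (assumed), the Regadenoson rate is 1 − (1 − background) × 0.75. Detection is then about 54% at 30% background (47.5% on drug), 49% at 40% (55%) and 37% at 60% (70%). With a fixed 20-point excess it stays near 60%. Recording everything and counting a pre-stated subset keeps the evidence without forcing all-cause counting.
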